**Intraoperative adjunctive antifibrotic therapy administered:**

- Compound/product, mode of administration, dose and concentration, timing of adjunctive agent (surgery day and pre- and postsurgical procedure/implantation)

**Visual parameters recovery post surgery:**

- Best corrected visual acuity (BCVA) with current glasses (preoperative and postoperative Day 1, Weeks 1 and 2, and Months 1, 3, 6, 9, and 12)
- Manifest refraction (baseline and postoperative Months 1, 3, 6, and 12)
- Surgically induced astigmatism (autorefractor reading [preoperative and postoperative Months 1, 6, and 12] and, at selected sites, topography [preoperative and postoperative Week 1 and Months 1 and 12])
- Optical biometry (anterior chamber depth and keratometric values [preoperative and postoperative Day 1 and Week 2]) at selected sites.

**Other:**

- Bleb morphology (anterior segment optical coherence tomography [AS-OCT] and slit lamp photography at selected sites).

**Safety:**

- Clinical hypotony defined as vision reduction (2 lines or more) related to macular changes consistent with hypotony maculopathy (macular folds), optic disc edema, and/or serous choroidal detachments because of low IOP
- Eyes with IOP 6 mm Hg or less at any time point and relevant clinical assessment (vision reduction [2 lines or more] related to macular changes consistent with hypotony maculopathy [macular folds], optic disc edema, anterior chamber status, and/or serous choroidal detachments because of low IOP) of these eyes at those time points
- Adverse events (AEs) including specific intraoperative and postoperative events of interest
- BCVA, pachymetry, visual field
- AE including serious AEs (SAEs)
- Adverse device effects (ADEs) including serious ADEs (SADEs)

**Patient-reported Outcomes:**

- Patient-reported Outcomes (PRO)

**Sample Size:**

The trial is intended to demonstrate that XEN is comparable to trabeculectomy in terms of treatment success rate. The sample size calculation is based on an equivalence test.

To control Type-I error rate at 5% and to attain 80% power for demonstrating that the difference is within the equivalence limit of 18%, about 256 study eyes will be needed for the study with a randomization ratio of 2:1 for the XEN arm: trabeculectomy arm. Allowing a 10% dropout rate for the first year, approximately 285 study eyes (190 for the XEN arm and 95 for the trabeculectomy arm) will need to be recruited for the study.

**Statistical Analysis:**

Four analysis populations will be used:

- Enrolled population: all study eyes for which the subject has signed the ICF

- Intent-to-treat (ITT) population: all enrolled eyes randomized to study glaucoma surgery (XEN or trabeculectomy)
- Modified Intent-to-treat (mITT) population: eyes in the ITT population that receive study glaucoma surgery and have no major protocol deviations
- Safety population: all enrolled eyes that undergo study glaucoma surgery, whether surgery is completed or aborted, and have follow-up visits or evaluations

The ITT population will be the primary effectiveness analysis population; some effectiveness analyses will also be run with the mITT population. All safety analyses will be run with the Safety population. Descriptive statistics (such as mean, SD, minimum, median, and maximum) will be presented for each continuous variable. Categorical variables will be displayed using frequency counts and percentages.

The number and proportion of subjects achieving  $\geq 20\%$  mean IOP reduction from baseline at Month 12 on the same or fewer number of topical IOP-lowering medications, without clinical hypotony, loss of vision to count fingers, or a secondary glaucoma surgical intervention will be tabulated with 95% CI calculated by using the normal approximation method. The difference of the proportions will be estimated and the 95% CI of the difference will also be calculated with the method of normal approximation. The 2 treatment arms will be claimed as equivalent if the 95% CI of the differences is within the -18% to 18% interval. The least squares mean change from baseline in IOP and the least squares mean difference between the 2 treatment groups will be estimated using the analysis of covariance (ANCOVA) model or the mixed-effect model repeat measurement (MMRM) model. The proportion and the 95% CI of complete success and qualified success will be calculated with normal approximation. All reported treatment-emergent AEs and all safety measures collected will be tabulated by counts and percentages.

---

4	TABLE OF CONTENTS	
1	Protocol Approval Signatures .....	2
2	Study Personnel .....	3
3	Synopsis .....	4
4	Table of Contents.....	9
5	List of Abbreviations and Definition of Terms.....	12
6	Introduction .....	14
6.1	Overview of Glaucoma.....	14

## 5 LIST OF ABBREVIATIONS AND DEFINITION OF TERMS

### LIST OF ABBREVIATIONS

ABiC	ab-interno canaloplasty
ACIOL	anterior chamber intraocular lens
ADE	adverse device effect
AE	adverse event
ANCOVA	analysis of covariance
AS-OCT	anterior segment optical coherence tomography
BCVA	best corrected visual acuity
CAI	carbonic anhydrase inhibitors
CIGTS	Collaborative Initial Glaucoma Treatment Study
CME	cystoid macular edema
CRO	contract research organization
eCRF	electronic case report form
EDC	electronic data capture
ETDRS	Early Treatment Diabetic Retinopathy Study
FDA	Food and Drug Administration
GATT	gonioscopy-assisted transluminal trabeculotomy
GCP	Good Clinical Practice
GPS	Gold-standard Pathway Study
HIPAA	Health Insurance Portability and Accountability Act
ICE	iridocorneal endothelial
ICF	informed consent form
ICH	International Council on Harmonisation
IEC	independent ethics committee
IOP	intraocular pressure
IOL	intraocular lens
IRB	institutional review board
ITT	intent-to-treat
MedDRA	Medical Dictionary for Regulatory Activities
MIGS	microinvasive glaucoma surgery
mITT	modified intent-to-treat
MMRM	mixed-effect model repeat measurement
MTMT	maximal tolerated medical therapy
n	number of subjects with an observation
N	number of subjects in the dataset or population
PACG	primary angle-closure glaucoma
POAG	primary open-angle glaucoma
PRO	patient-reported outcomes
RTSM	Randomization and Trial Supply Management
SADE	serious adverse device effect
SAE	serious adverse event
SAP	statistical analysis plan
SHPC-18	Symptom and Health Problem Checklist (18 items)
SLT	selective laser trabeculoplasty
SOP	standard operating procedure
UC3	ultrasonic circular cyclocoagulation
WHO	World Health Organization

WPAI            Work Productivity and Activity Impairment  
XEN            XEN-45 Gel Stent

## 6 INTRODUCTION

### 6.1 Overview of Glaucoma

Glaucoma is the leading cause of irreversible vision loss worldwide. Although several eye conditions are variants of glaucoma, the most common types of glaucoma are primary open-angle glaucoma (POAG) and primary angle-closure glaucoma (PACG). Asia accounts for a disproportionate number of PACG cases, whereas the prevalence of POAG is more evenly distributed throughout the world (Quigley 1996).

The goal in the treatment of glaucoma is to prevent further loss of functional vision during the remainder of a patient's life and to avoid an adverse impact on the patient's quality of life (AAO Glaucoma PPP Panel 2015).

There are many known risk factors for glaucoma including age, ethnicity, and family history. Intraocular pressure (IOP) is the only modifiable risk factor that is currently available to arrest visual field loss and reduction of IOP has been shown to reduce the risk of glaucomatous visual field loss in many landmark trials.

The prevention of glaucomatous loss of vision is mainly achieved by lowering the eye pressure to a threshold that is deemed to be safe for the ganglion cells given the current amount of damage in the optic nerve head (ie, target IOP).

There are many approaches to lower IOP including pharmacotherapy (topical and systemic), laser therapy, and surgery. Topical medications are often the first line of treatment, especially in early disease along with selective laser trabeculoplasty (SLT). Most patients require multiple medications to lower IOP to target (AAO Glaucoma PPP Panel 2015).

Traditional incisional glaucoma surgery results in robust IOP lowering; however, the accompanying side effects often preclude use earlier in the treatment paradigm. Trabeculectomy is the gold standard and currently the most commonly used drainage procedure, but complications are a major problem. Early and late complications include bleb leak, excessive drainage, flat anterior chamber, filtration failure, clinical hypotony, symptomatic blebs, bleb encapsulation, filtration failure, hyphema, choroidal effusion, suprachoroidal hemorrhage, and bleb infection (Gedde et al. 2007). Complications associated with drainage surgeries can have serious consequences and require careful management to prevent further problems. The bleb is currently the cornerstone of trabeculectomy drainage surgery, but the trabeculectomy bleb is also fragile and susceptible to scarring (Azura-Blanco and Katz 1998). Another subconjunctival surgical approach includes the Ex-PRESS® miniature glaucoma implant (Alcon Laboratories Inc., Fort Worth, TX), which is a biocompatible, nonvalved stainless steel tube. The Ex-PRESS is currently implanted using a procedure like standard trabeculectomy, and includes creation of a sclera flap and a conjunctival filtration bleb, but no peripheral iridectomy is required when implanting the Ex-PRESS (Moisseiev et al. 2015).

---

Trabeculectomy and tube shunt surgeries have an important role in glaucoma management, offering the ability to achieve IOP lowering independent of patients' compliance in appropriate candidates. Tube shunts are being increasingly used in the surgical management of glaucoma. The Ahmed glaucoma valve and the Baerveldt implant represent the most commonly used tube shunts. The Ahmed valve has a valve mechanism to prevent postoperative hypotony and shallow anterior chambers, whereas the Baerveldt implants provide a greater surface area in the end plate for aqueous reabsorption, providing better IOP control and a reduced need for glaucoma medication over the long term (Gedde et al. 2010, Wang et al. 2016). All the above procedures, performed using an ab-externo approach, achieve lowering of IOP via drainage of aqueous from the anterior chamber to the subconjunctival space (Gedde et al. 2012). However, each of these procedures is associated with a lengthy and variable recuperation and prolonged time to visual recovery. In some instances, there is associated loss of best corrected visual acuity (BCVA) and significant risk of short- and long-term complications, including hypotony, choroidal effusion, cataract, and flat or shallow anterior chamber, as well as valve-related complications, such as tube blockage, erosion, and endothelial cell loss (Gedde et al. 2012, Shaarawy et al. 2004, Rulli et al. 2013, Vijaya et al. 2011).

An alternative option to the more invasive traditional surgeries described above, in the form of microinvasive glaucoma surgery (MIGS) devices, are now available that have an improved safety profile and recovery compared with trabeculectomy and tube shunts (Saheb and Ahmed 2012). There are several devices fitting the definition of MIGS including XEN-45 Gel Stent (XEN); they can be categorized by their intended mechanism of action, ie, they may improve outflow by targeting the trabecular meshwork or the supraciliary space (Caprioli et al. 2015). Unlike canal-based and supraciliary MIGS devices, XEN facilitates subconjunctival drainage like the gold-standard surgical option trabeculectomy to provide robust IOP lowering from a medicated baseline (Vera et al. 2018, Mansouri et al. 2018, Hengerer et al. 2017).

Topical therapy is often the first line intervention for IOP lowering in open-angle glaucoma. Although the standard practice is to prescribe a second IOP-lowering medication when the first drug has lowered a patient's IOP, but not to an optimal level, the efficacy seen with monotherapy may not translate into similar efficacy when a medication is used adjunctively. Additionally, the side effects of multiple medications need to be considered for patient quality of life (Fechtner and Singh 2001).

To quantify the IOP reduction after surgery in clinical trials versus topical IOP-lowering medications, a consistent definition of the baseline, or reference IOP is necessary. For practical purposes, the highest challenge for a trial is the maximal tolerated medical therapy (MTMT) of IOP-lowering medications because that level would be considered the best that those drugs can achieve (Shaarawy et al. 2004). To determine the MTMT for glaucoma and the amount of medication an eye can tolerate, patients may need to endure severe adverse effects before advancing to surgery. In contrast, in clinical practice, the goal is optimal medical therapy, in which the practitioner uses the least amount of medicine to achieve the desired goal with the least adverse effects. In

standard clinical practice, ophthalmologists prescribe at least 2 glaucoma medications before suggesting surgical intervention to a patient. After treatment failure with the second, and certainly after the third medication is added, it is unlikely that additional agents will improve the outcome (Fechtner and Singh 2001).

## **6.2 XEN Gel Stent**

### **6.2.1 Device Description**

A MIGS drainage device implanted via an ab-interno approach that facilitates drainage of aqueous from the anterior chamber to the subconjunctival space (XEN-45; Allergan, Irvine, CA) has recently been approved in the United States for use in the surgical management of glaucoma. This device, which can be used as a standalone procedure, offers the potential to achieve IOP lowering that is comparable to trabeculectomy, but with less tissue manipulation (Schlenker et al. 2017, Reitsamer 2016).

The device, which is implanted using a handheld disposable injector, is constructed from porcine-derived gelatin that is formed into a tube and cross-linked with glutaraldehyde, thus allowing it to expand and remain flexible when hydrated. The expansion of the tube's outer diameter, when in contact with fluid, also aids in retention of the gel stent in its intended location after surgical implantation, which helps minimize many of the issues associated with other materials, such as migration, erosion, and corneal endothelial damage (Aref and Varma 2012). The gel stent was designed using principles established by the Hagen–Poiseuille equation, whereby outflow resistance to the fluid increases linearly in proportion to the length of the tube, and decreases to the fourth power of the diameter of the tube lumen. In sum, a longer and thinner tube provides greater resistance than a shorter and wider tube (Sheybani et al. 2015).

The XEN Gel Stent, XEN-45, or XEN Gel Implant (XEN) is indicated for the management of refractory glaucomas, including cases in which previous surgical treatment has failed, cases of POAG, and cases of pseudoexfoliative or pigmentary glaucoma with open angles that are unresponsive to MTMT.

### **6.2.2 Clinical Experience**

XEN is the first ab-interno minimally invasive procedure that creates a new pathway for aqueous flow from the anterior chamber to the subconjunctival space. Clinical studies have shown XEN is effective at reducing IOP with fewer complications as compared with those published for trabeculectomy studies (Schlenker et al. 2017, Mansouri et al. 2018, Hengerer et al. 2017, DeGregorio et al. 2018, Grover et al. 2017).

## 7 STUDY OBJECTIVES

To compare the effectiveness and safety of XEN to trabeculectomy in subjects with glaucoma refractory to topical medical therapy defined as intraocular pressure (IOP) not at target on 1 or more topical medications.

### 7.1 Primary Endpoint

Percentage of subjects achieving  $\geq 20\%$  mean IOP reduction from baseline at Month 12 on the same or fewer number of topical IOP-lowering medications, without clinical hypotony, loss of vision to count fingers, or secondary glaucoma surgical intervention.

### 7.2 Secondary Endpoints

Effectiveness:

- Mean and changes in mean IOP and number of topical IOP-lowering medications from preoperative baseline over time
- Change from baseline (medicated) in mean IOP and mean number of topical IOP-lowering medications at Month 12
- Proportion of eyes achieving specific IOP targets ( $\leq 18$  mm Hg,  $\leq 17$  mm Hg,  $\leq 16$  mm Hg,  $\leq 15$  mm Hg,  $\leq 14$  mm Hg,  $\leq 13$  mm Hg, and  $\leq 12$  mm Hg at Month 12)
- Proportion of eyes achieving specific percentage IOP lower targets from baseline ( $\geq 25\%$  to  $50\%$  in  $5\%$  increments)
- Proportion of eyes achieving  $\geq 20\%$  IOP reductions and specific IOP targets detailed above on same or lower number of topical IOP-lowering medications at Month 12
- Mean and changes in mean IOP and number of topical IOP-lowering medications from preoperative baseline over time in eyes with medicated baseline IOP  $\leq 18$  mm Hg
- Needling rates; number of needlings per eye; outcomes post needling, including mean IOP and number of medications measured by proportion of eyes achieving  $>20\%$  reduction at Month 12 on same or fewer topical IOP-lowering medications, and number of subjects not using any topical IOP-lowering medications; and antifibrotic use during needling.

Complete and qualified success:

- Complete success (IOP  $\leq 18$  mm Hg, with  $20\%$  or greater IOP lowering from medicated baseline on no topical medications) at Month 12 (eyes with clinical hypotony will be excluded)
- Qualified success (IOP  $\leq 18$  mm Hg with  $20\%$  or greater IOP lowering from medicated baseline with topical medications) at Month 12 (eyes with clinical hypotony will be excluded)

- Medication-free eyes, mean IOP in this cohort, and proportion of eyes at specific IOPs ( $\leq 18$  mm Hg,  $\leq 17$  mm Hg,  $\leq 16$  mm Hg,  $\leq 15$  mm Hg,  $\leq 14$  mm Hg,  $\leq 13$  mm Hg, and  $\leq 12$  mm Hg at Month 12)
- Proportion of eyes achieving specific percentage IOP lower targets from baseline ( $\geq 25\%$  to  $50\%$  in  $5\%$  increments) with medication-free eyes.

Intraoperative adjunctive antifibrotic therapy administered:

- Compound/product, mode of administration, dose and concentration, timing of adjunctive agent (surgery day and pre- and postsurgical procedure/implantation).

Visual parameters recovery post surgery:

- BCVA with current glasses (preoperative and postoperative Day 1; Weeks 1 and 2; and Months 1, 3, 6, 9, and 12)
- Manifest refraction (baseline and postoperative Months 1, 3, 6, and 12)
- Surgically induced astigmatism (autorefractor reading [preoperative and postoperative Months 1, 6, and 12] and, at selected sites, topography [preoperative and postoperative Week 1, and Months 1 and 12])
- Optical biometry (anterior chamber depth and keratometric values) at preoperative and postoperative Day 1 and Week 2 at selected sites.

Other:

- Bleb morphology (anterior segment optical coherence tomography [AS-OCT] and slit lamp photography at selected sites).

Safety:

- Clinical hypotony defined as vision reduction (2 lines or more) related to macular changes consistent with hypotony maculopathy (macular folds), optic disc edema, and/or serous choroidal detachments because of low IOP
- Eyes with IOP 6 mm Hg or less at any time point and relevant clinical assessment (vision reduction [2 lines or more] related to macular changes consistent with hypotony maculopathy [macular folds], optic disc edema, anterior chamber status, and/or serous choroidal detachments because of low IOP) of these eyes at those time points
- Adverse events (AEs) including specific intraoperative and postoperative events of interest
- BCVA, pachymetry, visual field
- AEs including serious AEs (SAEs)
- Adverse device effects (ADEs) including serious ADEs (SADEs)

Patient-reported Outcomes:

- Patient-reported Outcomes (PRO)

### **7.3 Exploratory Objective**

Not applicable.

## 8 INVESTIGATIONAL PLAN

### 8.1 Overall Study Design and Plan: Description

[figure not shown]
This is a multicenter, randomized, parallel-group, prospective, open-label clinical trial to compare the ability of XEN and trabeculectomy to reduce IOP and reduce the number of topical IOP-lowering medications in subjects with IOP that is poorly controlled on topical therapy.

Subjects will be randomized 2:1, resulting in approximately 190 eyes being implanted with XEN and approximately 95 eyes receiving trabeculectomy. Subjects will be screened for enrollment, and eligible candidates will be approached to ascertain interest in study participation. Duration of participation in the study will be approximately 12 months. The study design is depicted in [Figure 8-1](#).

If both eyes of a subject meet the study entry criteria, the study eye will be selected by the investigator.

#### 8.1.1 Study Design

**Figure 8-1 Flow Chart of the Study**

Note: These numbers are approximate.

#### 8.1.2 Schedule of Assessments

The schedule of planned study assessments is shown in [Table 8.1](#).

**Table 8.1 Schedule of Assessments**

Procedure / Data to be Recorded	Baseline Qualifying Visit a	Preoperative Visit 1 a	Operative		Postoperative Visits (visit window; time since Day 0)														
			Visit 2 Day 0	Visit 3 Day 1 (6-48 h)	Visit 4 Week 1 (3-10 d)	Visit 5 Week 2 (11-20 d)	Visit 6 Month 1 (3-8 wk)	Visit 7 Month 3 (9-17 wk)	Visit 8 Month 6 (18-32 wk)	Visit 9 Month 9 (33-47 wk)	Visit 10 Month 12 (48-60 wk)								
Demographics	X																		
Medical and Ophthalmic History	X																		
Subject Eligibility	X																		
Informed Consent/HIPAA	X																		
Concomitant Medications and/or Procedures Review	X	X		X	X	X	X	X	X	X	X	X	X	X	X	X	X	X	X
Intraocular Pressure (IOP)	X b	X		X	X	X	X	X	X	X	X	X	X	X	X	X	X	X	X
Autorefractor		X								X									
Visual Acuity (BCVA) c	X	X		X	X	X	X	X	X	X	X	X	X	X	X	X	X	X	X
Manifest Refraction	X									X	X	X	X	X	X	X	X	X	X
Biomicroscopy (slit lamp exam)	X	X		X	X	X	X	X	X	X	X	X	X	X	X	X	X	X	X
Gonioscopy Assessment (Schaffer's Scale) d	X			X d	X d	X d	X d	X d	X d	X d	X d	X d	X d	X d	X d	X d	X d	X d	X d
Visual Field Exam	X e																		
Ophthalmoscopy		X		X	X	X	X	X	X	X	X	X	X	X	X	X	X	X	X
Pachymetry		X																	
Topography f		X								X									
Biometry f		X		X	X	X	X	X	X	X	X	X	X	X	X	X	X	X	X
AS-OCT f				X	X	X	X	X	X	X	X	X	X	X	X	X	X	X	X
Bleb Photography f				X	X	X	X	X	X	X	X	X	X	X	X	X	X	X	X
PRO: SHPC-18 g				X	X	X	X	X	X	X	X	X	X	X	X	X	X	X	X
PRO: Postsurgical Question g																			
PRO: WPAI g	X							X											X
Randomization																			
Glaucoma Surgery																			X

Procedure / Data to be Recorded	Baseline Qualifying Visit a	Preoperative Visit 1 a	Operative		Postoperative Visits (visit window; time since Day 0)										
			Visit 2 Day 0	Visit 3 Day 1 (6-48 h)	Visit 4 Week 1 (3-10 d)	Visit 5 Week 2 (11-20 d)	Visit 6 Month 1 (3-8 wk)	Visit 7 Month 3 (9-17 wk)	Visit 8 Month 6 (18-32 wk)	Visit 9 Month 9 (33-47 wk)	Visit 10 Month 12 (48-60 wk)				
Record Needling and Laser Suture Lysis, and Antifibrotic Treatments			X	X	X	X	X	X	X	X	X	X	X	X	X
Adverse Events Assessment		X	X h	X	X	X	X	X	X	X	X	X	X	X	X

AS-OCT = anterior segment optical coherence tomography; BCVA = Best corrected visual acuity; d = day; h = hour; HIPAA = Health Insurance Portability and Accountability Act; IOP = intraocular pressure; PRO = patient reported outcome; SHPC-18 = Symptom and Health Problem Checklist; wk = week; WPAI = Work Productivity and Activity Impairment

a The Baseline Qualifying Visit and the Preoperative Visit may be done on the same day if there are no changes in preoperative IOP medications. The Preoperative Visit may be repeated to complete all procedures, if needed. The visit window for Preoperative Visit 1 (including any repeated visits) is up to 4 weeks before study glaucoma surgery in the study eye and  $\geq 3$  months since previous intraocular surgery in either eye.

b This is the medicated baseline IOP value. This should be performed at approximately the same time at each visit whenever possible. Subject has taken IOP medication.

c BCVA should be performed using a Snellen chart with glasses.

d Performed at Baseline Qualifying Visit and then at other times at the investigator's discretion

e Can use valid results up to 3 months prior to screening

f At selected sites only

g Patient questionnaires should be self-administered prior to any clinical assessments.

h Refers to intraoperative events or surgical complications

CONFIDENTIAL

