5.3.1. Definition of Primary Endpoint

The primary effectiveness endpoint is the proportion of responders meeting all criteria below:

- Achieving $\geq 20\%$ mean IOP reduction from baseline at Month 12
- No increase in number of topical IOP-lowering medications at Month 12 compared to the baseline
- No clinical hypotony
- No loss of vision to count fingers or worse
- No secondary glaucoma surgical intervention.

The IOP will be assessed at all study visits by standard Goldmann Applanation Tonometry. For each IOP assessment, two consecutive measurements will be taken for each eye. If these 2 measurements differ by > 1 mm Hg, a third measurement will be performed for the given eye. The IOP value for a given eye will be the average of all measurements, which will be obtained from the eCRF, and the percent change from baseline at Month 12 will be computed as

$$\text{Percent change} = \frac{\text{Month 12 IOP} - \text{Baseline IOP}}{\text{Baseline IOP}} \times 100$$

The subject having the computed value of ≤ -20 will be considered achieving $\geq 20\%$ mean IOP reduction from baseline at Month 12.

The usage of topical IOP-lowering medication will be collected in the concomitant medication page. The IOP-lowering medication that were started before the Month 12 visit and stopped on or after the Month 12 visit or recorded as ongoing will be considered as the medication taken at Month 12. The partial start and stop dates of the medication will be imputed based on missing dates imputation rules specified in Appendix 3.

The clinical hypotony is defined as vision reduction (2 lines or more) related to macular changes consistent with hypotony maculopathy (macular folds), optic disc edema, and/or serous choroidal detachments because of low IOP. The following steps provide the identification of a patient with clinical hypotony. A patient at any time point with the following conditions:

- 1- filter any eyes with IOP of 6 mmHg or less, from this list...
- 2- Filter any eyes with VA reduction 2 lines or more compare to baseline, from the eyes left (and this is where it becomes more clinical and difficult, but the n should not be too high at this point)...
- 3- Filter any eyes that reported on the "OPHTHALMOSCOPY CRF" abnormal macula or periphery; AND any eyes that reported any of these AE:
 - Anterior chamber shallow with peripheral irido-corneal touch
 - Anterior chamber flat with irido-corneal touch

CONFIDENTIAL

Draft Statistical Analysis Plan v2.0

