XEN-45 Gel Stent

- BCVA loss of ≥ 2 lines (≥ 10 ETDRS letters)
 - ≤ 30 days
 - > 30 days
 - At 12 months (persistent loss)
- Choroidal effusion (extending posterior to equator, without blood)
- Choroidal effusion (obscuring disc or macula, without blood)
- Choroidal effusion (with choroids touching in the center of the eye, without blood)
- Choroidal effusion (extending posterior to equator, with blood)
- Choroidal effusion (obscuring disc or macula, with blood)
- Choroidal effusion (with choroids touching in the center of the eye, with blood)
- Choroidal effusion and/or hemorrhage occurring > 30 days (persistent)
- Hypotony maculopathy
- Macular edema

The Best Corrected Visual Acuity (BCVA) should be performed using a Snellen Chart with glasses at all study visits. For participants with vision loss that Snellen Chart cannot be used, the vision acuity will be collected as Count Fingers, Hand Movement, Light Perception, or No Light Perception. Patients with vision loss to count fingers will be counted as not meeting the criteria.

The secondary glaucoma surgical intervention will be recorded in the glaucoma surgery eCRF page.

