5.6.3.3. Best Corrected Vision Acuity (BCVA)

BCVA will be performed using a Snellen chart with glasses, and the BCVA data collected in the visual acuity eCRF page will be analyzed. The line change from baseline at each follow-up evaluation will be calculated using the following formula:

$$\text{Line change} = 10 \times [\log_{10}(20/d_{\text{follow-up}}) - \log_{10}(20/d_{\text{baseline}})]$$

Where d_{baseline} = denominator of the Snellen equivalent unit at baseline

$d_{\text{follow-up}}$ = denominator of the Snellen equivalent unit at follow-up

The logarithmic values are to be rounded to the nearest tenth before calculation of the line change. A positive value indicates an improvement and a negative value indicates a worsening.

The data for the worst line change from baseline across follow-up will be summarized by treatment group for the study eye. The worst line change is defined as the greatest decrease from baseline in the number of lines read. Summary statistics of the worst line change will be presented in each of the following categories: worsening (< -2), no change (≥ -2 and ≤ 2) and improving (> 2). The number and percentage of participants with study eye meeting criteria of each category will be presented.

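### The acuity labelled BCVA is read through current glasses at every visit, so refractive change after surgery can be scored as loss of best-corrected vision

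*Protocol*

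**What the plan says.** Footnote c to Protocol Table 8.1 gives the method: "BCVA should be performed using a Snellen chart with glasses". Protocol 7.2 is more specific about the correction and the visits: "BCVA with current glasses (preoperative and postoperative Day 1; Weeks 1 and 2; and Months 1, 3, 6, 9, and 12". The SAP repeats the method in 5.3.1 ("The Best Corrected Visual Acuity (BCVA) should be performed using a Snellen Chart with glasses at all study visits") and in 5.6.3.3 ("BCVA will be performed using a Snellen chart with glasses").

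Refraction is a separate item in Protocol 7.2: "Manifest refraction (baseline and postoperative Months 1, 3, 6, and 12". The plan also treats refractive change as an outcome: "Surgically induced astigmatism (autorefractor reading [preoperative and postoperative Months 1, 6, and 12".

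The with-glasses reading is then used as evidence of harm:

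- SAP 5.6.3.3 takes each eye's worst line change over follow-up and calls it worsening when it is below −2.
- Protocol 10.1.2.1.2 and SAP 5.6.2.1 list BCVA loss of 2 or more lines as an adverse event, with a category for persistent loss at 12 months.
- Step 2 of the clinical hypotony filter in SAP 5.3.1 reads "Filter any eyes with VA reduction 2 lines or more compare to baseline". Absence of clinical hypotony is one component of the primary responder definition.

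**The concern.** Acuity through the patient's existing spectacles is habitual acuity. It equals best-corrected acuity only while the spectacles still match the eye. Two incisional operations are being compared, and the plan itself expects astigmatism to change. Inclusion criterion 7 rules out anticipated ocular surgery, such as cataract surgery, only for the first 3 months, so later surgery could also change the refraction.

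No section asks for acuity through the new refraction, for pinhole acuity, or for a record of whether glasses were updated. A drop in the reading can therefore mean lost visual potential, an out-of-date prescription, or both. A later rise can mean recovery or new glasses. A safety table titled BCVA cannot separate these. At stake are the visual safety comparison between the operations and, in a narrow set of eyes, one component of the primary endpoint.

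**Working it through.** The plan states no figure for this point, so there is nothing to reproduce. The check has four parts.

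**1. Visits.** Acuity is taken at eight postoperative visits: Day 1, Weeks 1 and 2, and Months 1, 3, 6, 9 and 12. Refraction is taken at four of them (Months 1, 3, 6 and 12). The other four (Day 1, Weeks 1 and 2, Month 9) have none, and the worst-change rule draws on all eight.

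**2. What each threshold catches.** SAP 5.6.3.3 gives line change = 10 × [log10(20/d_follow-up) − log10(20/d_baseline)], with logs rounded to one decimal.

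| Baseline to follow-up | Unrounded | SAP value | Loss of 2 or more lines | Safety table |
|---|---|---|---|---|
| 20/20 to 20/30 | −1.76 | −2.0 | yes | no change |
| 20/20 to 20/40 | −3.01 | −3.0 | yes | worsening |
| 20/40 to 20/60 | −1.76 | −2.0 | yes | no change |
| 20/40 to 20/80 | −3.01 | −3.0 | yes | worsening |

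The safety table therefore needs about 3 rounded lines, while the adverse event and filter step 2 need 2. The SAP does not say that step 2 uses this formula; I have assumed it does.

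**3. How often blur could reach those thresholds.** The documents give no refractive data. I assume a normally distributed uncorrected shift with mean 0 and SD 0.5, 0.75 or 1.0 D, and d = 0.25 or 0.5 D per line. I also assume no error through the glasses at baseline, a shift in either direction counting as loss, and glasses never updated. Then P(loss of k or more lines) = 2 × [1 − Φ(k × d / SD)].

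| Threshold | d (D per line) | SD 0.5 | SD 0.75 | SD 1.0 |
|---|---|---|---|---|
| k = 3 (safety table) | 0.25 | 13% | 32% | 45% |
| k = 3 (safety table) | 0.5 | 0.3% | 4.6% | 13% |
| k = 2 (adverse event, step 2) | 0.25 | 32% | 50% | 62% |
| k = 2 (adverse event, step 2) | 0.5 | 4.6% | 18% | 32% |

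Equal SDs in the two arms give a between-arm gap of zero. SDs of 0.5 and 0.75 D give a gap at k = 3 of 18.4 points (0.25 D per line) or 4.3 points (0.5 D per line).

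**4. Reach into the primary endpoint.** The filter in SAP 5.3.1 has these conditions:

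- step 1: IOP of 6 mm Hg or less;
- step 2: acuity loss of 2 or more lines;
- step 3: abnormal macula or periphery on ophthalmoscopy, and a listed adverse event.

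One of the listed events is BCVA loss of 2 or more lines. A single spectacle reading can thus meet step 2 and the adverse-event part of step 3. The IOP and fundus conditions remain as independent checks.

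To see how sensitive the result is, take the SAP's 68 and 34 completers and assume 48/68 and 24/34 responders (70.6% each, close to the SAP's 0.70). The difference is 0. The standard error is √(0.706 × 0.294/68 + 0.706 × 0.294/34) = 0.0957, and the lower 95% limit is −1.96 × 0.0957 = −18.8%. One false failure changes the difference by −1/68 = −1.5 points if in XEN and by +1/34 = +2.9 points if in trabeculectomy. Three in XEN move the lower limit to −23.4%, and four move it to −24.95%, past the −24% margin in SAP section 2. Two in trabeculectomy move it to −13.5%. How many such eyes there would be is unknown.

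**The case against.** The strongest reply is that acuity with current glasses is an openly stated choice. Both documents list it under visual recovery after surgery, where functional acuity is a reasonable measure, with refraction and induced astigmatism reported beside it. The BCVA safety summary is descriptive and carries no hypothesis test. Nothing forbids updated glasses at later visits, and footnote c says only that glasses are worn. The clinical hypotony definition also ties the vision loss to macular, disc or choroidal findings caused by low IOP.

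Most of this stands, and it limits the point. Misclassification can occur; it is not certain. Keeping the with-glasses reading as a recovery measure is sound. The reply does not cover the reuse of that reading, under the name BCVA, as evidence of lost best-corrected vision, when the refraction needed for a true BCVA is already scheduled at half of the postoperative visits.

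A reader might go further and infer that blur by itself creates primary-endpoint failures. The filter does not allow that, because low IOP and a fundus finding are also needed. The wording of step 3 could be read as pooling eyes with a fundus finding and eyes with a listed event. I read it as requiring both, which fits the definition stated just before it. Low IOP would be needed on either reading.

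**Conclusion.** The point holds as a measurement defect that should be corrected, with limited reach into the primary endpoint. That the reading is taken with current glasses, is not linked to refraction, and is used in three harm classifications rests on the text alone.

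The frequencies are illustrations: 13% to 45% or 0.3% to 13% for the safety-table threshold, depending on dioptres per line. They rest wholly on assumed inputs, and the model leans towards overstatement by treating every shift as loss and glasses as never replaced.

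A reader might also infer a bias against one arm from the statement in Protocol 6.2.1 that XEN disturbs less tissue. The documents do not support this. That statement says nothing about refraction, equal refractive spread gives no gap, and false hypotony failures would move the primary comparison in opposite directions depending on the arm. Neither the size nor the direction of any between-arm bias can be derived.

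**What to change.** - At the Baseline Qualifying Visit and Months 1, 3, 6 and 12, record Snellen acuity through the manifest refraction already scheduled.
- Use that value as BCVA for the line change in SAP 5.6.3.3, for persistent loss at Month 12, and for the vision step of the hypotony filter at those visits. Name the Baseline Qualifying Visit value as its baseline, because SAP 5.1 generally takes baseline from Preoperative Visit 1 while refraction is done at the qualifying visit.
- Keep the with-glasses readings at all visits and label them *acuity with current glasses*. Summarise their worst line change separately, against the with-glasses baseline. This keeps the early visits in the safety report.
- At Day 1, Weeks 1 and 2 and Month 9, continue to use the with-glasses reading for the hypotony vision step, and say so.
- Where refracted acuity was not recorded, relabel the data and flag 2-line losses that coincide with a change in manifest refraction.

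The cost is one extra acuity field, two acuity summaries instead of one, and SAP wording; no visit or procedure is added. Four of the eight postoperative visits would still have only habitual acuity. SAP version 2.0 is dated May 2021, so refracted acuity not captured at past visits cannot be recovered. The documents do not show whether the refraction form already holds it.
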